1.0 GOALS AND OBJECTIVES (SCIENTIFIC AIMS)

Primary Aim:

1.1

To identify the ^{131}I -MIBG treatment regimen associated with the highest overall response rate after one course of treatment on the following three arms: single-agent ^{131}I -MIBG; vincristine / irinotecan / ^{131}I -MIBG; or vorinostat / ^{131}I -MIBG

Secondary Aim:

1.2

To compare the toxicity profiles associated with each of the following three ^{131}I -MIBG treatment regimens: single-agent ^{131}I -MIBG; vincristine / irinotecan / ^{131}I -MIBG; or vorinostat / ^{131}I -MIBG

Exploratory Aims:

1.3

To describe best overall response for patients treated with two courses of therapy, site-specific response of bone marrow, soft tissue, and MIBG-avid lesions as well as overall survival and progression-free survival following each of three ^{131}I -MIBG treatment regimens

1.4

To assess peripheral blood and bone marrow minimal residual disease at study entry and following each of three ^{131}I -MIBG treatment regimens quantified using a neuroblastoma-specific NB 5-gene detection assay (NB5 assay) by TaqMan[®] low density array (TLDA)

1.5

To compare whole body radiation exposure in patients with neuroblastoma treated with each of three ^{131}I -MIBG treatment regimens

1.6

To evaluate peripheral blood lymphocyte γ -H2AX foci levels, expression of a panel of DNA damage response genes in peripheral blood mononuclear cells, plasma Flt-3 ligand, serum amylase, and circulating tumor DNA as markers of radiation exposure, response, and toxicity in patients with neuroblastoma treated with each of three ^{131}I -MIBG treatment regimens

1.7

To evaluate the performance of a computerized MIBG scan scoring system in patients with relapsed or refractory neuroblastoma treated with ^{131}I -MIBG therapy

1.8

To evaluate the association between tumor norepinephrine transporter (NET) protein expression and response to protocol therapy.

1.9

To describe the concordance rate between institutional Curie score and centrally reviewed Curie score in patients with relapsed or refractory neuroblastoma.

1.10

To describe the incidence and severity of sinusoidal obstruction syndrome (SOS) in patients with neuroblastoma who receive ^{131}I -MIBG therapy on this protocol and subsequently receive high-dose chemotherapy with stem cell rescue as part of their clinical care.

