7.0 REQUIRED OBSERVATIONS/MATERIAL AND DATA TO BE ACCESSIONED

7.1 Clinical and Laboratory Studies

Blood and urine studies must be performed within 2 weeks of study enrollment. Tumor disease evaluation (including appropriate imaging studies, bilateral bone marrow aspirate and biopsy for standard histology and urine catecholamines) are required within 3 weeks of study entry and subsequent to any prior therapy. Echocardiogram and ECG are required within 4 weeks of study entry and subsequent to any prior therapy. Initiation of protocol therapy is required within 1 week of study enrollment.

References to second course of therapy in the following table are only relevant to patients enrolling prior to Amendment 7A.

OBTAIN OTHER STUDIES AS NEEDED FOR GOOD PATIENT CARE.

Observation	Before Entry	Days -1 to +7 of Each Course ¹	Days 8 to 43 of each Course	Day 43 to 50 of each Course
Physical Exam ⁵ (Ht, Wt, BSA, VS) Performance status only at entry	X	Day 4 (+/- 1 day)	Every other week	X
CBC, Diff, Platelets ⁵	X	Day 4 (+/- 1 day)	Twice weekly ²	X
AST, ALT ⁵ , Total ⁵ + Direct Bilirubin, Albumin	X	Day 4 (+/- 1 day)	Weekly	X
BUN, Serum Creatinine ⁵	X	Day 1 prior to MIBG infusion for Vorinostat Arm Only and Day 4 (+/- 1 day) for All Patients	Weekly	X
PT/INR and PTT ⁵	X	Weekly on Vorinostat Arm	Weekly on Vorinostat Arm	X
Electrolytes, Calcium, Magnesium, Phosphorus	X	Day 4 (+/- 1 day)	Weekly	X
T ₄ , TSH	X			X
Serum β-HCG ^{3,5}	X			X
MUGA or Echocardiogram ⁵	X			X
Electrocardiogram ⁵	X	Vorinostat Arm Only: Day 4 (+/- 2 days)		X (Vorinostat Arm Only)
Urinalysis	X			X
Urine catecholamines VMA/HVA	X			X
Bilateral BM Aspirate + Biopsy for morphology ^{4, 7}	X			X
Blood and Marrow for N04-05	X			X
Anatomic imaging (CT or MRI scan) of chest/abdomen/pelvis plus any other known sites of measurable disease ⁴	X			X
MIBG diagnostic scan (REQUIRED) ^{4, 5} Use same isotope with each scan	X			X
MIBG whole body scan		On release from radiation isolation		
Whole body dosimetry		Days 1 to 4 ⁶		
Blood for biology studies (if consent)		See Section 8	See Section 8	
Archival slides for biology studies (if consent)		See Section 8		

1. No other routine bloodwork/radiology studies are required while patient is hospitalized unless clinically indicated. Patients with prior electrolyte imbalance should be monitored during the hydration.
2. Continue until ANC $> = 500$ cells/ μ L and platelet count $> = 20,000$ cells/ μ L x 3 days without transfusion then weekly until Day +43.

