10.4 Toxicity Evaluation

Toxicity is the secondary endpoint of this trial. All patients who begin treatment with vincristine, irinotecan, vorinostat, or ¹³¹I-MIBG will be evaluable for toxicity. Toxicity will be graded using the CTCAE criteria, version 4.0 which can be downloaded from the CTEP home page (<http://ctep.cancer.gov>).

Patients will undergo standard screening for toxicity used in previous NANT ¹³¹I-MIBG studies. All patients who begin study therapy will be evaluable for toxicity. All toxicities will be tabulated and reported according to received treatment arm. Differences in the incidence of toxicities between treatment arms will be assessed using the Fisher’s exact test.

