10.6.4 Monitoring plan for other toxicities

In addition to monitoring for delayed engraftments and toxic deaths, we will formally summarize the toxicities experienced at the time of the first interim futility analysis (20 patients per arm). The vincristine/irinotecan and the vorinostat arms will each be compared to the single-agent MIBG arm. Differences in the occurrence of Grade 3+ non-hematologic toxicities that are significant at the 0.10 level (two-sided Fisher's exact test) at the time of the first interim futility analysis will be flagged for further evaluation. The results of the interim analyses will be reviewed by the NANT Study Management Committee, reported to NANT DSMB and a decision in consultation with NANT DSMB will be made to close the trial, modify the trial, or continue unchanged.

Every 6 months, reports are prepared for DSMB review. These reports will summarize toxicities experienced which will allow an assessment of the safety for the trial overall, as well as each of the 3 arms individually. We do not plan to calculate p-values for every single type of toxicity, but the data summaries will permit identification of unexpected patterns in terms of severity or frequency.

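### Section 10.4 tests QTc and INR/PTT findings between arms, although Section 7.1 looks for them far more often on the vorinostat arm

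*Combined protocol and SAP*

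**What the plan says.** Aim 1.2, the secondary aim, is "To compare the toxicity profiles associated with each of the following three" regimens. Section 10.4 states that "All toxicities will be tabulated and reported according to received treatment arm", and that "Differences in the incidence of toxicities between treatment arms will be assessed using the" Fisher's exact test. It gives no alpha and no restriction to particular events. On detection it says only this: "Patients will undergo standard screening for toxicity used in previous NANT" MIBG studies. It does not mention that the schedule differs by arm.

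The observation table in Section 7.1 does differ by arm:

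- **PT/INR and PTT:** at entry and Day 43-50 on all arms. In both periods between, the entry is "Weekly on Vorinostat Arm".
- **ECG:** at entry on all arms. During treatment the entry is "Vorinostat Arm Only: Day 4 (+/- 2 days"), and the Day 43-50 ECG is also for that arm only. Section 4.6 likewise asks for an ECG before a second course only on the vorinostat arm.
- **BUN and creatinine:** "Day 1 prior to MIBG infusion for Vorinostat Arm Only and Day 4 (+/- 1 day) for All Patients", then weekly and at Day 43-50 on all arms.

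Note 1 to the table requires no other routine blood work in hospital unless clinically indicated, so Arms A and B have no scheduled substitute. Blood counts, AST/ALT, bilirubin, albumin, electrolytes and physical examination follow one schedule on all arms.

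**The concern.** An incidence comparison assumes that an event had a similar chance of being recorded in each arm. A prolonged QTc without symptoms cannot be found on Arm A or B by any scheduled test after entry, and a transient INR or PTT abnormality can be found there only at Day 43-50. Fisher's test treats a patient who was not tested as a patient without the event.

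The error runs one way, against vorinostat. Section 2.4.6 reports grade 3 QTc prolongation in the preceding vorinostat study, so a QTc difference here would be easy to take as confirmation. Section 10.1 makes the choice of winner depend on toxicity and tolerability as well as response, so what the secondary comparison appears to show has a use.

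**Working it through.** **Plan's figure.** The plan gives no operating characteristics for the toxicity tests. The only figure needed is the arm size, 35, which Section 10.5 ties to an 80% chance of selecting the best arm when it is 15 points better. In an exact calculation without interim looks, 35 per arm gives 79.4% if ties count as failures and 82.6% if ties are broken at random. The arm size is therefore consistent with its stated basis.

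**Scheduled checks after entry, from Section 7.1, one course**

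| Test | Arm C | Arms A and B |
|---|---|---|
| PT/INR, PTT | 1 (Days -1 to 7) + 5 (weekly, Days 8-43) + 1 (Day 43-50) = 7; 6 to 8 depending on how weeks are counted | 1 |
| ECG | 1 (Day 4) + 1 (Day 43-50) = 2 | 0 |
| Creatinine | 1 (Day 1) + 1 (Day 4) + 5 (weekly) + 1 (Day 43-50) = 8 | 7 |

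**Assumptions.** The chance q that one check shows a recordable abnormality is the same in every arm, so there is no true difference. The documents give no value for q; 2%, 5% and 10% are shown. Alpha is taken as 0.05, two-sided.

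**Step 1, independent checks.** The chance of at least one recorded abnormality in k checks is 1 - (1 - q)^k. For INR/PTT at q = 5%:

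- Arm C: 1 - 0.95^7 = 0.302, or 35 × 0.302 = 10.6 patients.
- Arm A or B: 0.05, or 35 × 0.05 = 1.8 patients.

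At q = 2% the incidences are 13% and 2%; at q = 10% they are 52% and 10%. Summing the two binomial distributions over all 35 v 35 tables with Fisher p ≤ 0.05 gives the rejection rates in step 2.

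**Step 2, correlated checks.** Repeated coagulation tests in one patient are unlikely to be independent, so the calculation was repeated with a beta-binomial model and within-patient correlation r.

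| INR/PTT, 7 v 1 checks: trials with p ≤ 0.05 and no true difference | q = 2% | q = 5% | q = 10% |
|---|---|---|---|
| r = 0 (independent) | 19% | 75% | 97% |
| r = 0.3 | 2% | 20% | 51% |
| r = 0.5 | 0.4% | 7% | 22% |

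For comparison, seven independent checks in both arms give 1.9%, 2.8% and 2.4%; one check in both arms gives 1.3% or less. The expected incidences stay unequal even where few trials reach significance: at q = 5% and r = 0.5 they are 12% and 5%. Counting six checks instead of seven lowers the 75% to 61%.

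**Step 3, ECG, 2 v 0 checks.** At q = 5%, Arm C is expected to show 1 - 0.95^2 = 9.8% and Arms A and B 0%. With independent checks, spurious significance occurs in 0.2%, 12% and 68% of trials at q = 2%, 5% and 10%. Six of 35 against 0 of 35 already gives p = 0.025. Correlation lowers the rates, but scheduled testing on Arms A and B still yields zero.

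**Step 4, creatinine, 8 v 7 checks.** At q = 5% the incidences are 34% and 30%, with rejection in 3.6% of trials against 2.9% with eight checks in both arms. This is negligible.

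**The case against.** The case on the other side has several parts.

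- **The extra tests are there for safety.** Agreed. The point concerns which findings enter a between-arm test, not who is monitored.
- **The scope is narrow.** This stands. A reader might infer that the whole secondary objective is compromised. The documents do not support that: most laboratory tests and the examinations share one schedule, and myelosuppression and diarrhea, prominent toxicities of these regimens, are not touched. Severe or symptomatic events, and tests done because clinically indicated, would be captured in every arm. The Day 1 creatinine adds one check to seven and can be set aside.
- **The large percentages rest on independence.** This stands too. Section 3.2.10.6 admits patients with INR or PTT up to 1.5 (times the upper limit, for PTT), so a mild abnormality may persist within a patient. At r = 0.5 and q = 2%, the rejection rate is below nominal.
- **Section 10.6.4 limits p-values.** The statement that p-values will not be calculated for every toxicity concerns the six-monthly reports. It does not restrict Section 10.4.
- **The interim flag should be left alone.** Correct. A reader might want the same restriction there. That flag covers "Differences in the occurrence of Grade 3+ non-hematologic toxicities that are significant at the 0.10 level", with about 20 patients per arm, and leads to further evaluation rather than a conclusion. At the lower rates expected for Grade 3+ events it would rarely fire falsely: even with independent checks, about 0.8% for INR/PTT at q = 1% and 0.1% for ECG at q = 2%. For a safety screen, excess sensitivity is the lesser error.
- **Testing only the Day 43-50 INR/PTT value would equalize the checks.** It would, but Section 4.2.3.1 ends vorinostat on Day 12, so that test would miss the period of exposure. Descriptive reporting is better.

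**Conclusion.** The point holds for two groups of terms: QTc prolongation and INR/PTT abnormalities found by scheduled testing. For these, Section 10.4 as written gives a comparison biased against vorinostat, and for QTc there are no scheduled comparator data after entry.

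The direction follows from the schedule alone. The size does not: for INR/PTT, spurious significance ranges from 0.4% to 97% over q of 2% to 10% and correlation of 0 to 0.5. It should not be quoted as a single figure, and 75% or 97% should not be read as the expected false-positive rate. The figures also assume the full 35 per arm and an alpha that the plan does not state.

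A reader might infer that a spurious p-value could cost the vorinostat arm its selection. The documents do not say so: Section 10.1 calls for a judgement on feasibility, and no Fisher result enters the selection rule. What is at stake is what the secondary objective may conclude about these terms. That justifies a change of wording, not of design.

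**What to change.** In Section 10.4, add:

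1. Between-arm Fisher tests apply to toxicities assessed on the same schedule in all three arms.
2. QTc and INR/PTT findings detected by scheduled testing are reported descriptively by arm, with the number of scheduled assessments shown and no between-arm test.
3. Clinically apparent or treated events, such as bleeding or arrhythmia, remain counted and compared in every arm.

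Keep all creatinine data in the comparison. Leave the monitoring schedule in Section 7.1 and the interim flag in Section 10.6.4 unchanged.

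The cost is a few sentences, with no new data or visits. The small downside is that these few laboratory and ECG terms are described rather than tested.

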10.5 Sample Size and Study Duration

While we expect that both the vincristine/irinotecan and the vorinostat arms will demonstrate higher response rates compared to the MIBG-alone arm – and that the selection therefore will only involve those

two arms – we have included the MIBG-alone arm to calibrate the improvement and better understand the impact of these chemotherapy additions. However, for purposes of determining the number of required patients, we will consider that all three arms are candidates of selection (i.e. could result in the highest observed response rate). The number of patients (35 per MIBG regimen, if no arms are dropped as inferior) was calculated to ensure an 80% chance that the regimen with the highest response rate is selected – if in fact that response rate is at least 15% better than the other two (using the methods described by Sobel and Huyett¹¹⁴ and summarized by Bechhofer, Santner and Goldsman¹¹⁵). Because we have incorporated Bayesian criteria for dropping an inferior arm or stopping early, the power of correct selection and other design characteristics were determined by simulation (see Appendix VIII for more details).

Table A in Appendix VIII summarizes the probability of correct selection, the probability of dropping one arm for futility, the probability of dropping the superior arm for futility, and the average number of patients in the inferior arm.

Estimates of the number of available patients for this study are derived from previous ¹³¹I-MIBG studies at NANT ¹³¹I-MIBG institutions. Specifically, NANT01-02 accrued 50 patients with refractory disease over approximately 40 months of active patient recruitment. NANT04-06 accrued 26 patients with relapsed or refractory disease over the approximately 40 months during which that study was open. This accrual rate underestimates the number of available patients given that NANT04-06 was a phase I study that utilized a 3+3 dose escalation strategy and accrual was closed for a minimum of 6 weeks after the third patient at each dose level was treated. CHOP, Cincinnati Children's, UCSF, and the University of Michigan treat 25, 12, 12, and 7 patients per year on their respective expanded access ¹³¹I-MIBG protocols. Newer NANT MIBG centers now include Children's Hospital Boston, Cook Children's Hospital, Children's Hospital of Colorado, Hospital for Sick Children, and Seattle Children's Hospital. These newer centers will increase access to MIBG treatment slots.

We therefore conservatively estimate that 4 patients per month will be available for enrollment in the current study. This accrual rate will allow completion of the study within 30 months, assuming all three regimens accrue a total of 35 patients/arm (i.e. interim futility analysis does not result in early closure of one of the arms). In order to account for potentially ineligible or inevaluable patients, a maximum of 115 patients are anticipated to enroll to yield 105 eligible and evaluable patients.

10.6 Monitoring Plan for Toxicity

Although we expect all three regimens to be generally well tolerated, several steps and procedures are in place in this trial, to monitor toxicities and safety. These are summarized briefly here and described more fully in the subsections below. All toxicities observed will be reported and summarized in the final report. The steps described below were developed for ongoing monitoring.

- (1) Delayed engraftment after reduced stem cell dose. Until the 1st 6 patients who receive a stem cell dose of only $1.5 - 1.9 \times 10^6$ CD34+/kg, demonstrate timely engraftment without problems (Section 10.6.1), all patients must have a stem cell dose of at least 2.0×10^6 CD34+/kg, or must have a back-up aliquot.
- (2) Monitoring delayed engraftment. Throughout the conduct of the trial, the details of any patient who fails to achieve timely engraftment will be formally reviewed (Section 10.6.2).
- (3) Monitoring for toxic death. Each death during treatment or within 2 months of stem cell infusion will be formally reviewed (Section 10.6.3).
- (4) Monitoring plan for other toxicities. Summaries are created every 6 months for review by the study PI and by the NANT DSMB. In addition, at the time of the 1st interim futility analysis, toxicities will be formally compared (Section 10.6.4).

10.6.1 Monitoring plan for delayed engraftment after reduced stem cell dose

Previous NANT ¹³¹I-MIBG trials (NANT N04-06 and N07-03) utilized a slightly higher minimum stem cell dose (2.0×10^6 CD34+ cells/kg) than planned for the current trial (1.5×10^6 CD34+ cells/kg). In order to evaluate the safety of this lower stem cell dose within this context, patients planning to receive a stem cell dose of $1.5 - 1.9 \times 10^6$ CD34+/kg must have a back-up aliquot of $1.5 - 1.9 \times 10^6$ CD34+/kg available until a minimum of 6 patients have been rescued with a stem cell dose of $1.5 - 1.9 \times 10^6$ CD34+/kg without delayed engraftment. If the first 6 patients receiving this reduced stem cell dose do not have delayed

engraftment, then future patients may enroll with only a minimum of 1.5×10^6 CD34+ cells/kg and no back-up aliquot. If any of the first 6 patients have delayed engraftment, then the required stem cell dose will be changed to 2.0×10^6 CD34+ cells/kg.

Patients planning to receive a stem cells dose of 2.0×10^6 CD34+/kg are not required to have a back-up aliquot at any time during the study.

10.6.2 Monitoring plan for delayed engraftment

Any time a patient fails to engraft (as defined in Section 4.7), the status of the study will be examined. Information reviewed will include the specific details of the patient whose engraftment was delayed, as well as the engraftment patterns of the other patients to date. A decision will be made by the NANT Study Management Committee, whether to report immediately to the DSMC or to include the information in the next DSMC report (within 6 months).

10.6.3 Monitoring plan for toxic death

Any time that a patient dies while undergoing treatment prior to a stem cell infusion, or within two months of stem cell infusion, the status of the study will be examined. Information reviewed will include the specific details of the patient who died, the timing of the death, the specifics of all patients who experienced the same type of toxicity that did not lead to death, and all toxicities observed to date.

Each death on study not due to tumor will be reviewed by the NANT Study Management Committee, reported to NANT DSMB and a decision in consultation with NANT DSMB and IND sponsor will be made to close the trial, modify the trial, or continue unchanged. In addition, it will be determined if the event requires that new information be added to the informed consent. Each death occurring within 30 days of completing the last dose of either ^{131}I -MIBG or vorinostat, whichever occurs last, regardless of cause will be reviewed and reported to the NANT DSMB and to the FDA according to standard procedure.

10.6.4 Monitoring plan for other toxicities

In addition to monitoring for delayed engraftments and toxic deaths, we will formally summarize the toxicities experienced at the time of the first interim futility analysis (20 patients per arm). The vincristine/irinotecan and the vorinostat arms will each be compared to the single-agent MIBG arm. Differences in the occurrence of Grade 3+ non-hematologic toxicities that are significant at the 0.10 level (two-sided Fisher's exact test) at the time of the first interim futility analysis will be flagged for further evaluation. The results of the interim analyses will be reviewed by the NANT Study Management Committee, reported to NANT DSMB and a decision in consultation with NANT DSMB will be made to close the trial, modify the trial, or continue unchanged.

Every 6 months, reports are prepared for DSMB review. These reports will summarize toxicities experienced which will allow an assessment of the safety for the trial overall, as well as each of the 3 arms individually. We do not plan to calculate p-values for every single type of toxicity, but the data summaries will permit identification of unexpected patterns in terms of severity or frequency.

10.7 Analysis of Correlative and Exploratory Studies

The correlative biology studies are considered descriptive. Based on prior NANT studies, we anticipate that a minimum of 80% of patients will agree to participate in studies that require additional blood sampling.

